13.13.17. Non-ICH Listings

Non-ICH : Listings					
No.	Population	IDSL / TST ID / Example Shell	Title	Programming Notes	Deliverable [Priority]
Study Population					
30.	ITT-E	ES2	Listing of Reasons for Maintenance phase Withdrawal		WK48, 96, EOS
31.	ITT-E	ES2	Listing of Reasons for Oral lead-in Period Withdrawal		WK48, 96, EOS
32.	ESP	ES2	Listing of Reasons for Extension phase Withdrawal		WK48, 96, EOS
33.	LTFU	ES2	Listing of Reasons for Long-term follow up Withdrawal		WK48, 96, EOS
34.	ITT-E	CM3	Listing of ART Medications Stopped Prior to Screening		WK48, 96, EOS
35.	ITT-E	CM3	Listing of ART Medications Received during Screening		WK48, 96, EOS
36.	ITT-E	CM3	Listing of ART Medications Received during LTFU phase		WK48, 96, EOS
37.	ITT-E	CM3	Listing of subjects with changes in Concomitant ARTs during Maintenance phase		WK48, 96, EOS
38.	ITT-E	CM3	Antiretroviral Therapy Taken Prior to & during Screening for Subjects Failing ART Eligibility Criteria	ART Eligibility Criteria are inc2, Exc 3, 4, 5, 6, 34, 36, 37. Please add footnote to this listing describing the details of these criteria (i.e. values of IETESTCD, IETEST)	WK48, 96, EOS
39.	ITT-E	Shell LSP11	Listing of Investigational Product Accountability		WK48, 96, EOS
Secondary Efficacy					
40.	CVF	Shell LSEF3	Listing of All Plasma HIV-1 RNA data for subjects with Confirmed Virologic Failure		WK48, 96, EOS
41.	ITT-E	Shell LSEF1	Listing of All Plasma HIV-1 RNA data for subjects with post-baseline viral load ≥ 50 c/mL		WK48, 96, EOS

Non-ICH : Listings					
No.	Population	IDSL / TST ID / Example Shell	Title	Programming Notes	Deliverable [Priority]
42.	ITT-E	Shell LSEF1	Listing of Plasma All HIV-1 RNA data for subjects with post-baseline viral load ≥ 50 c/mL at Oral lead-in period		WK48
43.	ITT-E	Shell LSEF5	Listing of HIV-1 Associated Conditions at Maintenance + Extension Phase		WK48, 96, EOS
Safety (The Safety listings below list data for Maintenance + Extension Phases, unless otherwise specified)					
44.	Safety	ABC_HSR_EXPO2	Listing of Abacavir Hypersensitivity Reaction Record - Exposure to Abacavir		WK48, 96, EOS
45.	Safety	ABC_HSR_DRUG2	Listing of Abacavir Hypersensitivity Reaction Record - Subject History of Drug Allergies		WK48, 96, EOS
46.	Safety	ABC_HSR_COND2	Listing of Abacavir Hypersensitivity Reaction Record - Subject and Family Conditions		WK48, 96, EOS
47.	Safety	ABC_HSR_RASH2	Listing of Abacavir Hypersensitivity Reaction Record - Skin Rash Details		WK48, 96, EOS
48.	Safety	ABC_HSR_SYMP4	Listing of Abacavir Hypersensitivity Reaction Record - Symptoms		WK48, 96, EOS
49.	Safety	VS4	Listing of Abacavir Hypersensitivity Reaction Record - Vital Signs		WK48, 96, EOS
50.	Safety	ABC_HSR_SYMP6	Listing of Abacavir Hypersensitivity Reaction Record - Individual Symptoms and Diagnostic Category Assignments (Excluding Other Symptoms)		WK48, 96, EOS
51.	Safety	ABC_HSR_SYMP7	Listing of Abacavir Hypersensitivity Reaction Record - Individual Symptoms and Diagnostic Category Assignments (Other Symptoms)		WK48, 96, EOS
52.	Safety	LIVER5	Listing of Liver monitoring/stopping Event reporting		WK48, 96, EOS
53.	Safety	LIVER6	Listing of Liver Event Information for RUCAM Score		WK48, 96, EOS
54.	Safety	LIVER7	Listing of Liver Biopsy Details		WK48, 96, EOS
55.	Safety	LIVER8	Listing of Liver Imaging Details		WK48, 96, EOS

CONFIDENTIAL

201585

Non-ICH : Listings					
No.	Population	IDSL / TST ID / Example Shell	Title	Programming Notes	Deliverable [Priority]
56.	Safety	Liver13	Listing Subjects Meeting Hepatobiliary Lab Criteria post-baseline at Maintenance Phase	Please also add those additional items shown in the summary of subjects meeting hepatobiliary lab criteria post-baseline (i.e. AST >3xULN and ALP <2xULN and BIL >=2xULN]; ALT+AST>=xx)	WK48
57.	Safety	AE8	Listing of Adverse Events Potentially Related to Torsades de Pointe		WK48, 96, EOS
58.	Safety	EG3	Listing of ECG values for subjects with Adverse Events Potentially Related to Torsades de Pointes		WK48, 96, EOS
59.	Safety	Liver13	Listing Subjects Meeting Hepatobiliary Lab Criteria post-baseline at Maintenance + Extension Phase for Q4W arm		WK48, 96, EOS
60.	ESP	Liver13	Listing Subjects Meeting Hepatobiliary Lab Criteria post-baseline at Extension Phase (for Current ART arm)		WK48, 96, EOS
61.	Safety	Liver13	Listing Subjects Meeting Hepatobiliary Lab Criteria post-baseline at Oral lead-in Maintenance Phase (for Q4W arm)		WK48
62.	Safety	Latte2 WK96CDISC report	Listing of Each Subjects ALT, AST, Bilirubin (including total and direct Bilirubin), INR, and ALP for subject meeting Hepatobiliary Lab abnormality criteria	8.1037 (add AST, ALP, INR, and direct Bilirubin to the listing and only for subject meeting Hepatobiliary Lab abnormality criteria)	WK48, 96, EOS
63.	Safety	Latte2 WK96CDISC report	Listing of Investigational Product Exposure Data for Subject Receiving Oral Bridging	8.1038	WK48, 96, EOS
Virology (mock up below from study 200056\wk96cdisc), 'Study phase' will be added as a column to the listing.					
64.	ITT-E	Listing 9.1005	Listing of Replication Capacity in IN and PR/RT Region		WK48, 96, EOS

13.14. Appendix 14: IDMC

An IDMC was instituted to perform a triggered periodic review of the accumulating data based on confirmed virologic failures to ensure that subjects are not being sub-optimally treated. In addition, the IDMC will review a futility analysis when 50% of subjects will have reached their Week 24 visit.

A list of outputs required for each IDMC analysis was provided in the IDMC Charter, Section 12.3, Appendix C.

Data handling methods and derived data definitions will be the same as detailed in this RAP, unless otherwise stated.

13.14.1. Adhoc CVF

The number of subjects meeting Confirmed Virologic Failure (CVF) Criterion per the protocol will be monitored and may result in ad-hoc IDMC data reviews.

The Statistics Data Analysis Centre (SDAC) will be notified by the study virologist in writing every time a CVF occurs in either study. The SDAC will track the number of subjects past Week 4. The rate of CVF will be monitored against the thresholds specified in IDMC Charter Table 1 (See IDMC Charter, Section 3.5.2).

13.14.2. Futility Interim

An interim futility analysis for the purpose of review by the IDMC will be performed for this study when about 50% of subjects will have reached their Week 24 visit.

For this Futility Interim, the primary efficacy measure to be reviewed was the proportion of subjects presenting with HIV-1 RNA ≥ 50 copies/mL at 24 weeks using a Snapshot analysis. A futility rule based on the Bayesian posterior predictive probability approach was applied to assess the evidence that the Q4W IM treatment arm is non-inferior to the current antiretroviral regimen (Current ART) arm given the interim data, at a 6% non-inferiority margin.

13.14.2.1. Futility analysis

An interim analysis for the purpose of review by the IDMC will be performed.

A futility rule will assess the evidence that the CAB LA + RPV LA treatment arm is non-inferior to the control arm (CAR). This rule will use the interim data (50% completing Week 24) to calculate the Bayesian predictive probabilities that the CAB LA + RPV LA arm is non-inferior to the CAR arm. A 6% non-inferiority margin will be used for this study.

For this analysis of CAB LA + RPV LA snapshot 'HIV-1 RNA \geq 50' rate relative to CAR, let:

X_{CR}^I = number of snapshot 'HIV-1 RNA \geq 50' at interim in CAB LA + RPV LA arm,

N_{CR}^I = number of subjects on CAB LA + RPV LA arm at interim,

X_{CAR}^I = number of 'HIV-1 RNA \geq 50' at interim in Triumeq/current ART arm, and

N_{CAR}^I = number of subjects on Triumeq/current ART at interim.

Since the true response rate is unknown, prior distributions are placed on these parameters of interest to reflect current beliefs and balanced with acceptable decision criteria performance. Conjugate beta densities are assumed. Since we are anticipating rather large sample sizes at the interim, we simply chose Jeffrey's priors for the response rates (Beta(0.5,0.5)), leading to the posterior distributions on the response rates, based on the interim data:

$$P_{CR} \sim \text{Beta} (0.5 + X_{CR}^I, N_{CR}^I + 0.5 - X_{CR}^I),$$

$$P_{CAR} \sim \text{Beta} (0.5 + X_{CAR}^I, N_{CAR}^I + 0.5 - X_{CAR}^I).$$

The posterior predictive probability distribution of the final response data given the final sample sizes:

X_{CR}^F = number of snapshot 'HIV-1 RNA \geq 50' in the final dataset in CAB LA + RPV LA arm,

N_{CR}^F = number of subjects on CAB LA + RPV LA arm at the final analysis,

X_{CAR}^F = number of 'HIV-1 RNA \geq 50' in the final dataset in Triumeq/current ART arm

N_{CAR}^F = number of subjects on Triumeq/current ART arm at the final analysis.

The number of future observed 'HIV-1 RNA \geq 50' in each arm follows a beta-binomial distribution:

$$X_{CR}^F - X_{CR}^I | X_{CR}^I \sim \text{beta-binomial} (N_{CR}^F - N_{CR}^I, 0.5 + X_{CR}^I, 0.5 + N_{CR}^I - X_{CR}^I)$$

$$X_{CAR}^F - X_{CAR}^I | X_{CAR}^I \sim \text{beta-binomial} (N_{CAR}^F - N_{CAR}^I, 0.5 + X_{CAR}^I, 0.5 + N_{CAR}^I - X_{CAR}^I)$$

The posterior predictive probability (PPP) with a 6% for study individual study, is:

$$PPP = \sum_{X_{CR}^I, X_{CAR}^I} P(X_{CR}^F - X_{CR}^I | X_{CR}^I) P(X_{CAR}^F - X_{CAR}^I | X_{CAR}^I) I\left(\frac{\hat{p}_{CR} - \hat{p}_{CAR} - (0.06)}{\sqrt{\frac{\hat{p}_{CR}(1-\hat{p}_{CR})}{N_{CR}^F} + \frac{\hat{p}_{CAR}(1-\hat{p}_{CAR})}{N_{CAR}^F}}}\right) < -1.96)$$

where $\hat{p}_{CR} = \frac{X_{CR}^F}{N_{CR}^F}$, $\hat{p}_{CAR} = \frac{X_{CAR}^F}{N_{CAR}^F}$ and I is an indicator taking the value 0 or 1. If PPP is less than the targeted threshold (15%), this would signal an IDMC review for futility. [Table 22](#) shows the point at which a futility review would be triggered for a range of virologic failure rates on each arm for this study.

Table 22 Posterior predictive probability (PPP) of determining non-inferiority for individual study (50% subjects reaching wk24). Shaded cells denote the scenarios that would be below the 15% futility criteria (6% non-inferiority Margin).

PPP		No. (%) of 'HIV-1 RNA \geq 50' (per FDA Snapshot algorithm) on CAB LA+RPV LA , out of 143							
		7 (5%)	8 (6%)	9 (6%)	10 (7%)	11 (8%)	12 (8%)	13 (9%)	14 (10%)
No. (%) of 'HIV-1 RNA \geq 50' (per FDA's Snapshot) on Comparator arm, out of 143	0	17.3	6.1	1.5	0.3	0	0	0	0
	1 (1%)	30.6	14.5	5.5	1.7	0.4	0.1	0	0
	2 (1%)	43.8	25.3	12.2	5.0	1.7	0.5	0.2	0
	3 (2%)	57.3	38.0	21.8	10.7	4.6	1.8	0.6	0.2
	4 (3%)	68.5	50.5	32.9	18.9	9.6	4.3	1.8	0.7
	5 (3%)	77.8	62.3	45.0	29.1	16.8	8.8	4.2	1.8
	6 (4%)	85.0	72.5	56.8	40.5	26.2	15.4	8.3	4.1
	7 (5%)	90.3	80.8	67.6	52.2	37.0	24.0	14.3	7.8
	8 (6%)	93.9	87.1	76.7	63.2	48.3	34	22.1	13.3

13.15. Appendix 15: Variables Defined for Time to Event Analysis

TRDF Detailed steps		
The steps below are for the derivation of TRDF i.e. for the Kaplan-Meier analysis only.		
Condition	Censor Status	Event Description/AVAL
1. Subjects met CVF event criteria during the Maintenance Phase. (Based on derived CVF)	CNSR=0	EVNTDESC=CVF AVAL=Date of SVF* *: immediately preceding CVF.
2. Subjects with study withdrawal due to 'Lack of efficacy', 'Treatment related AE', 'intolerability due to injection', or 'protocol defined Safety stopping criteria' during Maintenance phase Note: primary reason for discontinuation based on Maintenance Conclusion Page. 'Treatment related AE' is defined as subjects that have primary reason for withdrawal =AE and that the subject has at least one AE considered drug related (AEREL=Y) and was withdrawn from study (AEWD=Y))	CNSR=0	EVNTDESC= terms in italic, respectively. For ART arm: AVAL= min (Date of Maintenance phase discontinuation, Date of Maintenance Current ART Stop Date + 1) For Q4W arm: AVAL= min [Date of Maintenance phase discontinuation, max(Date of Last Q4W IM Dose + 35, Last Oral dose Date + 1)] Note: Last Q4W IM / last oral dose/ Maintenance Current ART Stop Date is only applied to subjects who permanently discontinue from study treatment Note: Date of Maintenance phase discontinuation is from Maintenance phase Conclusion page
If none of the above conditions met		
3. subjects withdraw during Maintenance Phase	CNSR=1	EVNTDESC='Censored due to Study Discontinuation for Other Reasons' AVAL will be defined as the same as above 2
4 . others	CNSR=1	EVNTDESC='Censored due to data cutoff for analysis' AVAL = End date of on-treatment maintenance phase Which will be defined as below: For Q4W min [week 52 visit date, HAART start date, last contact date, max(date of last Q4W IM dose+35, last oral dose date+1)] For Current ART min [week 52 visit date, last contact date, Current ART stop date+1]

The same approach as will be used to define 'ERDF' except that the reason of withdrawal in Condition 2 will be restricted to 'Lack of Efficacy'.

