	Q4W IM Arm: For subjects continuing into Extension Phase: Maintenance Treatment Start Date < Date ≤ Date of Nominal Week 52 visit For subjects not continuing into Extension Phase: Maintenance Treatment Start Date < Date ≤ LTFU ART Start Date
Extension	Subjects Switching from Maintenance Current ART Arm to Q4W IM: Start Date of Extension Phase Oral lead-in of CAB + RPV < Date ≤ LTFU ART Start Date Subjects continuing maintenance Q4W IM into Extension phase Date of Nominal Week 52 Injection < Date ≤ LTFU ART Start Date

- Date = start or assessment date
- Maintenance Treatment Start Date: refer to Treatment Start Date in Section 13.6.1

Table 18 Assignment of Study Phases for Concomitant medication/ART

Concomitant during:	Date range
Maintenance	Current ART Arm: Maintenance Treatment Start Date ≤ Medication Taken < Start Date of Extension Phase Oral CAB + RPV (expected to be Nominal Week 52) or Withdrawn date prior to Extension Phase
	Q4W IM Arms: For subjects not continuing into Extension Phase: Maintenance Treatment Start Date ≤ Medication Taken < LTFU ART Start Date For subjects continuing into Extension Phase: Maintenance Treatment Start Date ≤ Medication Taken < Date of Nominal Week 52 visit
Extension	Date of nominal Week 52 visit ≤ Medication Taken < LTFU ART Start Date

Note: ART stopped on or before the Maintenance Treatment start date will not be assigned to the Maintenance Phase; ART stopped on or before the date of nominal Week 52 visit will not be assigned to Extension phase.

If a partial date for medication/ART is recorded in the eCRF, the following convention will be used to assign the medication:

- if the partial date is a start date, a '01' will be used for missing days and 'Jan' will be used for missing months;
- if the partial date is a stop date, a '28/29/30/31' will be used for the missing day (dependent on the month and year) and 'Dec' will be used for the missing month; for medications recorded separately in the eCRF as prior ART, the earlier of this imputed date or the day before IP start will be used.

The recorded partial date will be displayed in listings.

Table 19 Assignment to Long-Term Follow-Up Phase

Study Phase	Date range
Long-Term Follow-Up	Date > max(Last IM Injection Date, Last Oral Bridging End Date)

- Date = Assessment/Start Date

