
 When a measurement of plasma HIV-1 RNA is below the limit of quantification (i.e. 40 c/mL) and is qualitatively observable that will be denoted as a “Target Detected” measure, while HIV-1 RNA below the limit of quantification that is not qualitatively observable that will be denoted as “Target Not Detected”. Any measurements <40 c/mL characterised as “Target Non-Detected” or

“Target Detected” will be captured in the database.
 
 • Super low viral load will also be tested by BioMNTR lab for Viral loads below the limit of quantification at some visits (e.g. Week 48)

Treatment (TRDF) and Efficacy Related (ERDF) Discontinuation = Failure

 • The analysis of time to confirmed virologic failure (CVF) or discontinuation due to treatment related reasons (i.e., drug-related AE, intolerability of injections, protocol defined safety stopping criteria, or lack of efficacy) will censor subjects who have not met CVF criteria and are ongoing in the study, or who have discontinued for reasons other than those related to treatment. This will be the Treatment Related Discontinuation = Failure (TRDF) data. • Subjects who have not met CVF criteria and are ongoing in the study, or who have discontinued for reasons other than lack of efficacy, will be censored in the analysis of the Efficacy Related Discontinuation = Failure (ERDF) data. • Proportion of Participants without virologic (ERDF) or tolerability (TRDF) failure will be estimated using the Kaplan-Meier nonparametric method based on the time to ERDF or TRDF. The estimated proportion at Week 48 will be presented by treatment group, along with estimated difference in proportions between treatment groups and its associated two-sided 95% CI. The estimate of the standard error used to derive confidence intervals will be based on Greenwood’s formula [Kalbfleisch, 1980].

Observed Case Summary for Subjects per Viral Load Category by Visit (Maintenance Phase)

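### Appendix 15 counts a confirmed virologic failure anywhere in the Maintenance Phase, on or off treatment, but stops follow-up for everyone else no later than the end of on-treatment

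*SAP*

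**What the plan says.** Appendix 15 applies four conditions in order.

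- **Condition 1 (event).** "Subjects met CVF event criteria during the Maintenance Phase. (Based on derived CVF"). The time is "AVAL=Date of SVF", the suspected failure that immediately precedes confirmation. No treatment state is named.
- **Condition 2 (event, listed withdrawal reasons).** Current ART: "AVAL= min (Date of Maintenance phase discontinuation, Date of Maintenance Current ART Stop Date + 1"). Q4W: "AVAL= min [Date of Maintenance phase discontinuation, max(Date of Last Q4W IM Dose + 35, Last Oral dose Date + 1")].
- **Condition 3 (other withdrawals, censored).** "AVAL will be defined as the same as above 2".
- **Condition 4 (all others, censored).** "AVAL = End date of on-treatment maintenance phase", spelled out as a minimum that includes the last day of treatment cover.

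ERDF uses the same steps, with the Condition 2 reasons limited to lack of efficacy.

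Table 17 (Section 13.4.1) sets the Maintenance Phase for laboratory data. For a Q4W participant who does not continue into the Extension Phase, the range is "Maintenance Treatment Start Date < Date ≤ LTFU ART Start Date". For a Current ART participant who does not continue, there is a start and no upper limit. Table 20 (Section 13.4.2) then defines a post-treatment state within Maintenance for both arms.

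Section 13.6.4 has these Kaplan-Meier estimates reported at Week 48 by arm, with a between-arm difference and 95% CI.

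**The concern.** Condition 1 and Conditions 2 to 4 use different ends of follow-up. Conditions 2 to 4 stop when treatment cover ends, or earlier. Condition 1 can reach past that point, as far as the Maintenance Phase extends. Whether off-treatment time is used for a participant then depends on the outcome: it is used for those who rebound and discarded for those who do not. Kaplan-Meier estimation assumes that the length of follow-up is not decided by whether the event occurs.

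The second fault is the order. A participant with a Condition 2 discontinuation who later has an off-treatment failure meets Condition 1 first, so the later date replaces the earlier one. TRDF combines virologic failure and treatment-related discontinuation, and its time should be that of whichever comes first.

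At stake is the meaning of a reported between-arm difference and CI in which few events are likely, so that one or two added events would be visible.

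**Working it through.** The SAP gives no figure on this point, so there is nothing to reproduce. The check is a comparison of rules followed by an illustration of size.

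**1. Is there a period inside Maintenance but after treatment?**

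- Q4W, not continuing: on-treatment ends at the later of last injection + 35 days and last oral dose + 1 day (Table 20). Maintenance ends at LTFU ART start (Table 17). The period exists whenever LTFU ART starts after the on-treatment end.
- Current ART, not continuing: on-treatment ends at ART stop + 1 day, and Maintenance has no end. The period always exists.

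**2. Two participants who stop on the same day for the same unrelated reason**

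- No rebound: Condition 3 censors at the earlier of phase discontinuation and the on-treatment end.
- Rebound, with the suspected failure after the on-treatment end and both values inside Maintenance: Condition 1 gives an event at that later date.

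If the suspected failure itself is on-treatment and only the confirmation comes later, the event date lies inside the on-treatment period. The treatment-state mismatch therefore needs an off-treatment suspected failure.

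**3. How much off-treatment time is counted?**

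Hypothetical case: 10 participants are off treatment for 42 days and 2 have a suspected failure at day 21. Person-days from those who fail: 2 × 21 = 42. From the others: 8 × 42 = 336. The rule uses 42 of 378 person-days but both events.

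**4. Size per event**

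570 randomised 1:1 gives 285 per arm (Section 2.3). One added event is 1/285 = 0.35 percentage points.

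A product-limit simulation (400 runs, 285 participants, read at Day 337, the Week 48 target in Table 9) gives nearly the same. Its inputs are assumptions, not from the SAP: 4 on-treatment failures; 15 or 25 withdrawals for other reasons with treatment ending on days 60 to 289; and k off-treatment failures, each 7 to 42 days after the on-treatment end. Cells show the failure estimate in % for 15 / 25 withdrawals.

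| k | On-treatment only | As written | Everyone followed 42 days off treatment |
|---|---|---|---|
| 0 | 1.45 / 1.48 | 1.45 / 1.48 | 1.44 / 1.46 |
| 1 | 1.45 / 1.48 | 1.81 / 1.85 | 1.79 / 1.82 |
| 2 | 1.45 / 1.48 | 2.16 / 2.21 | 2.15 / 2.18 |
| 5 | 1.45 / 1.48 | 3.23 / 3.30 | 3.21 / 3.26 |
| 10 | 1.45 / 1.48 | 4.97 / 5.07 | 4.95 / 5.03 |

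The first off-treatment failure adds 0.36 to 0.37 points. The larger k only show that the effect is close to additive; they are not forecasts. The last two columns differ by 0.01 to 0.04 points, so nearly all the effect comes from turning a censoring into an event, and very little from missing time at risk.

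**5. Condition 1 ahead of Condition 2**

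For a participant who already meets Condition 2, Condition 1 adds no event but moves the date later. The number of events by Week 48 changes only if the move crosses Week 48.

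**The case against.** The strongest reply is that Condition 1 relies on a derived CVF, and Section 13.6.4 refers to Protocol Section 5.4.4 for its definition. That section is not at hand and may limit CVF to on-treatment samples. Section 13.3.1 also applies the Week 4 to Week 52 analysis visits only to on-treatment Maintenance data. This stands as a limit on certainty, but it does not repair the SAP text. The SAP's own CVF definition in Section 4 has no on-treatment limit, Section 13.3.1 concerns visit slotting, and Table 11 shows that the SAP says so expressly (for Snapshot) when it wants on-treatment data only.

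A second reply is that counting every CVF is a legitimate choice of estimand. The ERDF sentence in Section 13.6.4 under which those who "discontinued for reasons other than lack of efficacy, will be censored in the analysis of the Efficacy Related Discontinuation = Failure (ERDF) data" applies only to participants who have not met CVF criteria, so counting CVF first fits it. That is fair. But a choice to count off-treatment failures would need off-treatment follow-up for everyone, and Conditions 2 to 4 do not give it.

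Third, such events may be rare. Section 2.3 has Q4W discontinuers start HAART, and the Month 1 follow-up target in Table 12 (Day 30) falls before the 35-day boundary. The control arm's follow-up visit is conditional on ongoing AEs or laboratory abnormalities. This stands, and it is why no frequency is claimed.

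A reader might infer that the Q4W arm collects more of these events because its discontinuers are followed for at least 52 weeks. The SAP does not support that: Table 17 closes their Maintenance Phase at LTFU ART start, so later samples cannot trigger Condition 1.

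**Conclusion.** The inconsistency is real on the SAP's own wording, and minor. Condition 1 lets off-treatment time count only for participants who fail, and its place ahead of Condition 2 means that TRDF is not time to first event.

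The supported size is about 0.35 percentage points in an arm per off-treatment failure by Week 48, in a participant who would otherwise be censored. This assumes 285 per arm and that Protocol Section 5.4.4 does not already restrict CVF to on-treatment samples.

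A reader might infer that the between-arm difference is biased in a known direction. That cannot be derived. The off-treatment period opens 1 day after stopping Current ART but 35 days after the last injection, and only the Q4W period is closed by LTFU ART start. The effects need not cancel, but their net sign is unknown. A reader might also infer material distortion from a depleted risk set; the illustration puts that part at only 0.01 to 0.04 points.

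The reach is limited to Tables 2.14 and 2.15. Table 4 lists the Kaplan-Meier estimate as a summary, neither table is marked as a headline deliverable, and neither is part of the testing in Section 5.5. The primary Snapshot analysis uses on-treatment viral loads and is unaffected.

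**What to change.** Amend Condition 1 in Appendix 15, for both TRDF and ERDF, along these lines:

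- Count a CVF in the Maintenance Phase as an event only if its suspected failure is on-treatment per Table 20 and falls on or before the end-of-follow-up date used in Conditions 2 to 4. Otherwise go to the next row.
- Where more than one condition qualifies as an event, take the earliest date as AVAL.
- List off-treatment CVFs separately, by arm, with the treatment stop date and any replacement ART start date.

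Both limbs of the first item are needed. Conditions 2 and 3 can end follow-up at phase discontinuation, which may precede the last on-treatment day in Table 20.

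The cost is a short change to the SAP wording and one date condition in the derivation, plus one listing. No new data are needed. If on-treatment CVF was always intended, the change records it and prevents the literal rule from being programmed.
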